9.2.3. Pausing Rules

The investigators and the sponsor's medical monitor will review the safety of enrolled subjects on an ongoing basis. The sponsor's medical monitor will be involved in all discussions and decisions (see Section 12.4).

If any of the following events occur in any subject who received at least one dose of study vaccine in the study (at any site), that site investigator will halt the vaccination of further subjects and the sponsor's medical monitor will be notified immediately. The sponsor's medical monitor will then also inform all the other investigators to halt further vaccination as well.

1. Death in any subject considered at least possibly related to the study vaccine; *OR*
2. An anaphylactic reaction within 24 hours of vaccination or the presence of generalized urticaria within 72 hours of vaccination in any subject considered at least possibly related to the study vaccine; *OR*
3. A life-threatening or other serious adverse event in any subject considered at least possibly related to the study vaccine.

If any of the following events occur in subjects who received at least one dose of study vaccine in the study (across all sites), the sponsor's medical monitor will notify all investigators to halt vaccination of further subjects.

4. Three or more subjects experience a severe (grade 3) (non-serious) unsolicited adverse event (of the same type) considered to be related to any of the study vaccines that persists for 3 or more days; *OR*
5. Three or more subjects experience a persistent (upon repeat testing) severe (grade 3) (non-serious) abnormality (including unexplained hematuria) related to the same laboratory parameter and considered to be related to any of the study vaccines; *OR*
6. Three or more subjects experience the same severe (grade 3) (non-serious) solicited systemic reaction considered to be related to any of the study vaccines that persists for 3 or more days (subjective systemic reaction corroborated by study personnel).

For the events described above, the sponsor's medical monitor notifies the IDMC immediately. Dosing will be halted and health authorities will be notified. Within 3 business days, the IDMC will convene to review the available safety data as outlined in the charter and to discuss study suspension or discontinuation of further vaccination or to decide that vaccination may resume. If any pausing rule is met, and following the IDMC review it is deemed appropriate to restart dosing, a request to restart dosing with pertinent data must be submitted to health authorities as a request for a substantial amendment. Dosing can restart only after approval of a substantial amendment by the competent authority. The sites will be allowed to resume activities upon receipt of a written notification from the sponsor. The criteria for pausing will be re-set each time and the same criteria have to be met again to halt further vaccination. The communications from

the IDMC will be forwarded by the investigator to the Independent Ethics Committee (IEC)/Institutional Review Board (IRB) according to local standards and regulations and by the sponsor to relevant health authorities.

9.3. Immunogenicity Evaluations

9.3.1. Immunogenicity Endpoints

Secondary Endpoints:

Humoral immune response

- Binding antibody levels elicited by vaccination using EBOV GP ELISA at 21 days post boost.

Exploratory Endpoints:

Exploratory analyses may be performed to further investigate study vaccine-elicited immune responses. These may include, but might not be limited to, the following assays at selected time points:

Humoral immune response

- Binding antibody levels elicited by vaccination using EBOV GP ELISA at other relevant time points.
- Neutralizing antibody responses against the EBOV GP defined as the serum titer that is able to inhibit viral infection by a certain percentage (IC₅₀, IC₈₀ and/or IC₉₀) using virus neutralization assay.
- Binding and/or neutralizing antibody responses against Ad26 and/or MVA vector in ELISA and/or neutralization assays and against EBOV isolate in a neutralization test, if assays are available.
- Humoral immune responses to different EBOV GPs and/or filovirus GPs and/or TAFV NP, if assays are available.
- Molecular and functional characterization of study vaccine-elicited antibodies, which may include, but will not be limited to: kinetic studies, repertoire analysis, Fc characterization, isotype analysis and epitope mapping, if assays are available.

Cellular immune response

- The presence and functional capacity of T cells may be determined using pathogen-specific stimulation of PBMC with EBOV GP peptides using IFN- γ ELISpot assays. Cytokine-producing T cells can be quantified using ELISpot technology.
- Activation of CD4+ and CD8+ T cell subsets and their cytokine expression patterns may be determined by flow cytometry (intracellular cytokine staining [ICS]) after EBOV GP-specific stimulation of fresh and/or frozen PBMC (including, but not limited to, IFN- γ , interleukin [IL]-2, and tumor necrosis factor [TNF]- α).

- Cellular responses to filovirus GPs and/or TAFV NP, if assays are available.
- Phenotypic and functional analysis of B, T and/or natural killer (NK) cells and other immune cell populations.

9.3.2. Immunogenicity Assessments

Details on sample collection and handling are provided in Section 9.5. In case of insufficient blood sample volume to perform assays, the samples will be analyzed according to the following priority ranking (ranked in order of decreasing priority): 1) core secondary endpoints, 2) core exploratory endpoints and 3) additional exploratory endpoints.

Core Immunogenicity Assessments in Cohorts II and III

Table 4 provides an overview of the core immunogenicity assessments (humoral and cellular assays) in Cohorts II and III. Blood samples for core immunogenicity assessments for the evaluation of secondary and exploratory endpoints as planned by the sponsor will be collected at the time points indicated in the Time and Events Schedule.

Blood samples (10 mL) for assessment of humoral immune responses will be obtained from all subjects in Cohorts II and III. Blood samples (40 mL) for assessment of cellular immune responses will be obtained from subjects in Cohorts II and III at selected sites with the capabilities to process PBMC (targeted at 10% of all subjects).

Table 4: Overview of Core Immunogenicity Assessments in Cohorts II and III

Sample	Core Immunogenicity Assessments (non-exhaustive)	Assays (non-exhaustive)
Serum, all subjects from Cohorts II and III	Analysis of antibodies binding to EBOV GPs Analysis of neutralizing antibodies to EBOV GPs Analysis of binding and/or neutralizing antibodies to adenovirus and/or MVA Analysis of EBOV GP, Filovirus GPs and/or TAFV NP antibody characteristics, including IgG subtyping	ELISA Virus neutralization assay Adenovirus and/or MVA ELISA and/or neutralization assay Molecular antibody characterization
PBMC, subjects from Cohorts II and III at selected sites ^a	T-cell IFN- γ responses to EBOV GP Analysis of T-cell responses to EBOV GP, Filovirus GPs and/or TAFV NP (including CD4/8, IL-2, IFN- γ , TNF- α and/or activation markers)	ELISpot ICS

ELISA: enzyme-linked immunosorbent assay; ELISpot: enzyme-linked immunospot; ICS: intracellular cytokine staining; IFN: interferon; IgG: immunoglobulin G; IL: interleukin; TNF: tumor necrosis factor

^a With the capabilities to process PBMC (targeted at 10% of all subjects).

Specific Immunogenicity Assessments in Cohort I and Additional Immunogenicity Assessments in Cohort II

Table 5 provides an overview of the specific immunogenicity assessments in Cohort I. Blood samples for plasmablast response kinetics will be collected in Cohort I at the time points indicated in the [Additional Time and Events Schedule](#) for the determination of the optimal sampling time points of the B-cell response as part of the additional immunogenicity assessments in Cohort II in the UK.

Table 5: Overview of Specific Immunogenicity Assessments by Academic Consortium Partners in Cohort I

Academic Consortium Partner/Laboratory	Specific Immunogenicity Assessments	Max. Blood Volume per Sampling Point	No. of Subjects Targeted per Group
University of Oxford	Kinetics of B-cell response (B-cell ELISpot)	10 mL, PBMC	10
	Transcriptomics ^a	3 mL, Tempus™ tube	All ^a

^a Optional blood samples (for transcriptomics) only to be obtained from subjects who consent separately.

Table 6 provides an overview of the additional immunogenicity assessments in Cohort II. Blood samples for additional immunogenicity assessments for the evaluation of additional exploratory endpoints as planned by the academic consortium partners will be collected from subjects in Cohort II at the time points indicated in the [Additional Time and Events Schedule](#). Blood samples will be collected for DNA isolation (in the UK), transcriptomics (in both countries), and EBOV neutralization (in France) from all subjects in Cohort II. For the other assays listed in Table 6, blood samples will be collected from all subjects in Cohort II in the UK, but initially only 25 subjects per group will be targeted for analysis, while in France, blood samples will be collected from and analyzed in no more than 25 subjects in Groups 1 and 2 in Cohort II at selected sites. In addition, these ‘other’ assays have to be performed within the same 25 subjects per group in the UK and in France. PBMC and serum samples for exploratory immunogenicity assessments collected in France may be analyzed in the UK and vice versa.

Table 6: Overview of Additional Immunogenicity Assessments by Academic Consortium Partners in Cohort II

Academic Consortium Partner/Laboratory ^a	Potential Additional Immunogenicity Assessments	Max. Blood Volume per Sampling Point	No. of Subjects Targeted per Group
University of Oxford	DNA isolation ^b	2 mL, whole blood	All ^b
	Transcriptomics ^c	3 mL, Tempus TM tube	All ^c
	Repertoire sequencing Isolation of monoclonal Ab Plasmablast phenotyping	25 mL (10 mL pre-prime), PBMC	25 ^d
	Memory B-cell characterization	25 mL, PBMC	
	Fresh ICS	10 mL, whole blood/PBMC	
INSERM	EBOV neutralization	3 mL, serum	All
	Transcriptomics ^c	3 mL, Tempus TM tube	All ^c
	Fresh ICS	10 mL, whole blood/PBMC	25 ^{e,f}
	T cell proliferation	10 mL, PBMC	
	T cell phenotyping (including Tfh)	4 mL, PBMC	
	Cytokine profiling	3 mL, serum	
London School of Hygiene and Tropical Medicine ^f	NK cell analysis ^f	4 mL, PBMC and 2 mL, serum ^f	

Ab: antibody; No.: number; Tfh: T follicular helper

^a PBMC and serum samples for exploratory immunogenicity assessments collected in France may be analyzed in the UK and vice versa.

^b Optional blood sample (for DNA) only to be obtained from subjects who consent separately.

^c Optional blood samples (for transcriptomics) only to be obtained from subjects who consent separately.

^d Blood samples to be collected from all subjects in Cohort II in the UK, but initially only 25 subjects per group will be targeted for analysis.

^e Blood samples to be collected from and analyzed in no more than 25 subjects in Groups 1 and 2 in Cohort II at selected sites in France.

^f Blood sampling for NK cell analysis done in France, but analysis performed at London School of Hygiene and Tropical Medicine.

Buffy coats will be obtained from the National Blood Transfusion Service (UK) for use of the PBMC in the validation and control of the B-cell ELISpot and memory B-cell characterization.

9.4. Vaccine-induced Seropositivity

In general, uninfected subjects who participate in Ebola vaccine studies may develop Ebola-specific antibodies as a result of an immune response to the candidate Ebola vaccine, referred to as VISP. These antibodies may be detected in Ebola serologic tests, causing the test to appear positive even in the absence of actual Ebola infection. VISP may become evident during the study, or after the study has been completed. The potential of a study participant becoming PCR-positive after vaccination is being assessed in a Phase 1 study (VAC52150EBL1002).

Subjects should not donate blood during participation in the study (from the start of screening onwards, see Section 4.2).

Consent will be obtained to contact the doctors that the subject sees regularly, to let them know that the subject is taking part in this study. It is important for all of the subject's doctors to know that the subject may be administered experimental vaccines. Subjects participating in the study

will be provided with a "wallet (study) card" and instructed to carry this card with them for the duration of the study (see Section 12.3.1).

9.5. Sample Collection and Handling

The actual dates and times of sample collection must be recorded in the CRF or laboratory requisition form. Refer to the [Time and Events Schedule](#) and the [Additional Time and Events Schedule](#) for the timing and frequency of all sample collections.

Sample collection and processing will be performed by the study-site personnel according to current versions of approved standard operating procedures.

Instructions for the collection, handling, storage, and shipment of samples are found in the Laboratory Manual that will be provided. Collection, handling, storage, and shipment of samples must be under the specified, and where applicable, controlled temperature conditions as indicated in the Laboratory Manual.

10. SUBJECT COMPLETION/DISCONTINUATION OF STUDY VACCINATION/WITHDRAWAL FROM THE STUDY

10.1. Completion

A subject will be considered to have completed the study if he or she has completed all assessments at the 6-month post-boost visit (or Day 365 if no boost vaccination was administered) for subjects who received placebo or at the Day 365 visit for subjects who received active vaccine. A subject who agrees to participate in the roll-over study will be considered to have completed the study when he or she completed the last safety-related visit in the current study (VAC52150EBL2001) or when he or she has been followed for an additional 12 months (whichever comes first).

10.2. Discontinuation of Study Vaccination/Withdrawal From the Study

Discontinuation of Study Vaccination

If a subject's study vaccine must be discontinued before the end of the vaccination schedule, this will not result in automatic withdrawal of the subject from the study.

A subject's study vaccine (prime or boost) must be discontinued at the discretion of the investigator and after consultation with the sponsor for any of the events in Section 6.2.

A subject's study vaccine will be **permanently** discontinued in case any of the following listed criteria is met:

- The investigator believes that for safety reasons (eg, adverse event) it is in the best interest of the subject to discontinue study vaccine;
- The subject becomes pregnant;
- The subject has confirmed Ebola virus disease;

- The subject experiences any of the events in Section 6.3;
- The randomization code is broken by the investigator or the study-site personnel.

Subjects meeting any of the reasons listed above must not receive any further study vaccine, but should continue to be monitored for safety and for immunogenicity according to the protocol if this does not result in safety risks for the subject. In case of early discontinuation of study vaccine due to an adverse event, the investigator will collect all information relevant to the adverse event and safety of the subject, and will follow the subject to resolution, or until reaching a clinically stable endpoint.

Withdrawal From the Study

Each subject has the right to withdraw from the study at any time for whatever reason. The investigator should make an attempt to contact subjects who did not return for scheduled visits or follow-up. Although the subject is not obliged to give reason(s) for withdrawing early, the investigator should make a reasonable effort to ascertain the reason(s) while fully respecting the subject's rights.

A subject will be withdrawn from the study for any of the following reasons:

- Decision by the investigator to withdraw a subject for repeated failure to comply with protocol requirements;
- Decision by the sponsor to stop or cancel the study;
- Decision by local regulatory authorities and IEC/IRB to stop or cancel the study;
- Lost to follow-up;
- Withdrawal of consent;
- Death.

If a subject withdraws early from the study for any of the reasons listed above (except in case of death), early withdrawal assessments should be obtained per the assessments for the 21-day post-boost visit. A subject who wishes to withdraw consent from participation in the study will be offered an optional visit for safety follow-up (before formal withdrawal of consent), but the subject has the right to refuse.

If a subject is lost to follow-up, every reasonable effort must be made by the study-site personnel to contact the subject and determine the reason for discontinuation/withdrawal. The measures taken to follow up must be documented.

When a subject withdraws before completing the study, the reason for withdrawal is to be documented in the CRF and in the source document. Study vaccine assigned to the withdrawn subject may not be assigned to another subject. For subjects who withdraw from the study after randomization but before the prime vaccination, an additional subject will be enrolled who will receive the same vaccine regimen as the withdrawn subject. No additional subjects will be enrolled in case subjects withdraw from the study after receiving the prime vaccination.

10.3. Withdrawal From the Use of Research Samples

A subject who withdraws from the study will have the following options regarding the optional research samples or for storage of samples for future use:

- The collected samples will be retained and used in accordance with the subject's original informed consent for optional research samples or for storage of samples for future use.
- The subject may withdraw consent for optional research samples or for storage of samples for future use, in which case the samples will be destroyed and no further testing will take place. To initiate the sample destruction process, the investigator must notify the sponsor study site contact of withdrawal of consent for the optional research samples and to request sample destruction. The sponsor study site contact will, in turn, contact the biomarker representative to execute sample destruction. If requested, the investigator will receive written confirmation from the sponsor that the samples have been destroyed.

Withdrawal From the Optional Research Samples While Remaining in the Main Study

The subject may withdraw consent for optional research samples while remaining in the study. In such a case, the optional research samples will be destroyed. The sample destruction process will proceed as described above.

Withdrawal From Storage of Samples for Future Use While Remaining in the Study

The subject may withdraw consent for storage of samples for future use (refer to Section 16.2.5) while remaining in the study. In such a case, the samples will be destroyed as described above. Details of the sample retention for research are presented in the ICF.

11. STATISTICAL METHODS

Statistical analysis on subject information, safety and core immunogenicity data will be done by the sponsor or under the authority of the sponsor. A general description of the statistical methods to be used is outlined below. Specific details will be provided in the Statistical Analysis Plan (SAP). The analysis to estimate survival based on immunobridging methodology, linking NHP immune response data with human immune response data, will be described in a separate SAP.

Separately, data of specific and additional immunogenicity assessments, as outlined in Section 9.3.2, will be analyzed by the academic consortium partners. Specific details of these analyses will be provided in a separate SAP and reported separately from the Clinical Study Report.

Interim analyses may be performed as detailed in Section 11.6. The primary analysis will be performed when all subjects have completed the 6-month post-boost visit or discontinued earlier. This analysis will include 6-month post-boost safety and all available immunogenicity data up to this point. The final analysis will be performed when all subjects have completed the last study-related visit or discontinued earlier. Note: due to delays in scheduled boost vaccinations caused by study pauses, the primary and final analysis may be combined.

11.1. Analysis Sets

The Full Analysis set includes all subjects who were randomized and received at least one dose of study vaccine, regardless of the occurrence of protocol deviations. Safety data will be analyzed based on the Full Analysis set.

The Immunogenicity analysis set includes all randomized and vaccinated subjects, who have data from baseline and at least one post-vaccination immunogenicity blood draw.

The Per Protocol analysis set includes all randomized and vaccinated subjects, who received both the prime and boost (administered not more than 10 days outside the visit window) vaccinations, have immunogenicity data from baseline and at least one post-vaccination evaluable immunogenicity sample, and have no major protocol violations influencing the immune response.

The immunogenicity analysis will be based on the Per Protocol analysis set. As sensitivity analysis, the immunogenicity data will also be analyzed based on the Immunogenicity analysis set, provided more than 10% of subjects in the Immunogenicity analysis set are excluded from the Per Protocol analysis set.

11.2. Sample Size Determination

An originally planned sample size of 612 subjects (pooled across the 3 cohorts) includes 492 subjects randomized to receive Ad26.ZEBOV and MVA-BN-Filo (in Cohorts II and III) to substantially contribute to an overall safety database of the Ad26.ZEBOV and MVA-BN-Filo prime-boost regimen. In Cohort I, 30 subjects will receive Ad26.ZEBOV and MVA-BN-Filo in an open-label fashion. Randomization to Group 3 was stopped per Amendment 4 to focus on the schedules for which an indication will be sought.

As randomization to Group 3 was not resumed, the overall sample size was reduced to approximately 543 subjects (Group 1: 204, Group 2: 204, Group 3: 135), with approximately 469 subjects (Group 1: 174, Group 2: 174, Group 3: 121) to receive Ad26.ZEBOV and MVA-BN-Filo (in Cohorts II and III) prime-boost regimen. Enrollment in the entire study will be stopped per Amendment 5. Details on the impact on the power will be described in the SAP and/or Clinical Study Report.

The probability of detecting an adverse event in each of the groups, and total, is given in [Table 7](#), for various true incidence rates. In case a specific adverse event is not observed, the one-sided 97.5% upper confidence limit of the true incidence rate of this adverse event is less than 3.3%, 2.2% and 0.8% for sample sizes of 121, 174 and 499 (ie, total number of subjects in Cohorts I, II, and III to receive Ad26.ZEBOV and/or MVA-BN-Filo) subjects, respectively.

Table 7: Probability of Observing at Least One Adverse Event Given a True Adverse Event Incidence

True Adverse Event Incidence (%)	N=30	N=121	N=174	N=469	N=499
0.1	3%	11%	16%	37%	39%
0.5	14%	45%	58%	90%	92%
1.0	26%	70%	83%	99%	99%
2.5	53%	95%	99%	100%	100%
5.0	79%	100%	100%	100%	100%
10.0	96%	100%	100%	100%	100%

Having core immunogenicity response data available for 164 subjects per group (ie, 84 from Cohort II and 80 from Cohort III), the following pairwise differences in immune response (ELISA antibody levels against EBOV GP) between vaccine schedules in [Table 8](#) can be detected at any given time point, for a given variability in ELISA antibody levels. With the reduction in sample size in Group 3, the power to detect these pairwise differences is at least 80%.

Table 8: Magnitude of Pairwise Difference to be Detected Between Vaccine Regimens With Sample Size of 164 Subjects

Variability ELISA Antibody Levels (SD, log ₁₀ scale)	Detectable Difference (log ₁₀ scale) *
0.5	0.20
0.6	0.24
0.7	0.28
0.8	0.32
0.9	0.37
1.0	0.41
1.1	0.45
1.2	0.49

SD: standard deviation; * 90% power, 2-sided test, 5% significance level, accounting for multiple testing

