Optional blood samples for transcriptomics will be collected from subjects in Cohorts I and II (as part of the specific and additional immunogenicity assessments by the academic consortium partners, respectively) and who consent separately to the transcriptomics component of the study. Blood samples will be collected at the specified time points (see [Additional Time and Events Schedule](#)). The goal is to assess the ribonucleic acid (RNA) transcriptome (gene expression) in a systems vaccinology approach to identify differentially expressed genes which relate to the immunologic and safety phenotype of the response to Ad26.ZEBOV and MVA-BN-Filo, and for analysis of antibody genes.

If subjects provide separate consent, leftover blood samples will be stored for possible future scientific/genetic research. Subjects can withdraw consent for their samples to be used for future research at any time.

STATISTICAL METHODS

An originally planned sample size of 612 subjects (pooled across the 3 cohorts) includes 492 subjects randomized to receive Ad26.ZEBOV and MVA-BN-Filo (in Cohorts II and III) to substantially contribute to an overall safety database of the Ad26.ZEBOV and MVA-BN-Filo prime-boost regimen. In Cohort I, 30 subjects will receive Ad26.ZEBOV and MVA-BN-Filo in an open-label fashion. Recruitment in Group 3 was stopped per Amendment 4 to focus on the schedules for which an indication will be sought. Enrollment in the entire study will be stopped per Amendment 5. Details on the impact on the power will be described in the Statistical Analysis Plan (SAP) and/or Clinical Study Report. In case a specific adverse event is not observed, the one-sided 97.5% upper confidence limit of the true incidence rate of this adverse event is less than 3.3%, 2.2% and 0.8% for sample sizes of 121, 174 and 499 subjects (ie, total number of subjects in Cohorts I, II, and III to receive Ad26.ZEBOV and/or MVA-BN-Filo), respectively.

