Study Cohorts	Randomization Ratio (Active:Placebo)	Group 1 N=204	Group 2 N=204	Group 3* N=204	Cohort Total N=612	UK** N=321	France** N=291
Cohort I	-	10/0	10/0	10/0	30	30	-
Cohort II	14:1	84/6	84/6	84/6	270	135	135
Cohort III	10:3	80/24	80/24	80/24	312	156	156

Groups 1, 2 and 3: prime on Day 1, followed by boost 28, 56 or 84 days after prime, respectively; N: number of subjects to receive study vaccine (Ad26.ZEBOV, MVA-BN-Filo or placebo)

* Randomization to Group 3 was stopped per Amendment 4 to focus on the schedules for which an indication will be sought.

** Enrollment in the entire study (ie, UK and France) will be stopped per Amendment 5.

Subjects in each cohort were randomized at baseline (on Day 1) in a 1:1:1 ratio to Groups 1, 2 and 3 (ie, the vaccination schedule). A schematic overview of the study vaccination schedules is provided in [Table 2](#). Within each group in Cohort I, subjects will receive Ad26.ZEBOV and MVA-BN-Filo in an open-label fashion. Randomization in Cohorts II and III was stratified by country. Within each group in Cohorts II and III, subjects were randomized to receive the prime-boost vaccination with either Ad26.ZEBOV followed by MVA-BN-Filo, or placebo in a 14:1 and 10:3 ratio, respectively (see [Table 1](#)). Randomization in each group (for Cohorts II and III) was stratified further according to age at randomization (≤ 50 years, > 50 years), with at least 20%

(of the total of both cohorts) of subjects in the >50 years category. Note that enrollment will not be resumed.

Study-site personnel (except for those with primary responsibility for study vaccine preparation and dispensing), sponsor personnel and subjects in Cohorts II and III will be blinded to the study vaccine allocation until all subjects have completed the 6-month post-boost visit or discontinued earlier and the clinical database is locked. Refer to Section 5 for further details on blinding in case of interim analyses.

Table 2: Schematic Overview of Study Vaccination Schedules in the Three Groups Pooled Across Cohorts I, II and III

Group*	N	Prime		Boost	
		Day 1	Day 29	Day 57	Day 85
1	204	174	Ad26.ZEBOV	MVA-BN-Filo	
		30	placebo	placebo	
2	204	174	Ad26.ZEBOV		MVA-BN-Filo
		30	placebo		placebo
3**	204	174	Ad26.ZEBOV		MVA-BN-Filo
		30	placebo		placebo

N: number of subjects to receive study vaccine (Ad26.ZEBOV, MVA-BN-Filo or placebo)

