5. TREATMENT ALLOCATION AND BLINDING

Vaccine Schedule and Study Vaccine Allocation

Based on subject's availability and informed consent, a subject was enrolled in one of 3 cohorts at study entry. Central randomization was implemented in this study. At baseline, subjects were randomly assigned to 1 of 3 groups in a 1:1:1 ratio in Cohorts I, II, and III, and within groups randomly assigned to Ad26.ZEBOV and MVA-BN-Filo, or placebo in a 14:1 and 10:3 ratio in Cohorts II and III, respectively, based on a computer-generated randomization schedule prepared before the study by or under the supervision of the sponsor. The randomization within each group was balanced by using randomly permuted blocks and was stratified by country in Cohorts II and III. Randomization in each group (for Cohorts II and III) was stratified further according to age at randomization (≤ 50 years, > 50 years), with at least 20% (of the total of both cohorts) of subjects in the > 50 years category. Note that randomization to Group 3 was not resumed per Amendment 4 and that enrollment in the entire study will be stopped per Amendment 5. The interactive web response system (IWRS) assigned a unique code, which dictated the assignment and matching vaccination schedule for the subject. The requestor must use his or her own user identification and personal identification number when contacting the IWRS, and will then give the relevant subject details to uniquely identify the subject.

Blinding

Blinding procedures are not applicable for Cohort I (as all subjects will receive Ad26.ZEBOV and MVA-BN-Filo in an open-label fashion).

In Cohorts II and III, subjects and study-site personnel will be blinded to the study vaccine allocation within groups until the last subject of the study completes the 6-month post-boost visit or discontinues earlier and the clinical database is locked, except for unblinded qualified study-site personnel with primary responsibility for study vaccine preparation and dispensing, and not involved in any other study-related procedure. The study vaccines will be administered by a study vaccine administrator (see [Definitions of Terms](#)).

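### The zero-event safety limit of under 0.8% needs 460 vaccinees; the stopped trial has about 423 subjects in all, and the 499 behind the limit counts Cohort I twice

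*Protocol*

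**What the plan says.** Protocol section 11.2 starts from 612 planned subjects: 492 to receive active vaccine in Cohorts II and III, and 30 more in the open-label Cohort I. After Group 3 was closed under Amendment 4, "the overall sample size was reduced to approximately 543 subjects (Group 1: 204, Group 2: 204, Group 3: 135"; the plan is then one "with approximately 469 subjects (Group 1: 174, Group 2: 174, Group 3: 121) to receive Ad26.ZEBOV and MVA-BN-Filo (in Cohorts II and III".

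The same section gives one-sided 97.5% upper limits for an adverse event that is never seen. They are said to be below 3.3%, "2.2% and 0.8% for sample sizes of 121, 174 and 499 (ie, total number of subjects in Cohorts I, II, and III". The synopsis repeats them, "for sample sizes of 121, 174 and 499 subjects (ie, total number of subjects in Cohorts I, II, and III". Table 7 has columns for both 469 and 499.

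Two other places describe the counts per group. Table 2 in protocol section 3.1, titled "Schematic Overview of Study Vaccination Schedules in the Three Groups Pooled Across Cohorts I, II and III", shows 174 active and 30 placebo in each group. The immunogenicity paragraph of section 11.2 reads "Having core immunogenicity response data available for 164 subjects per group (ie, 84 from Cohort II and 80 from Cohort III".

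On the halt in enrolment under Amendment 5, section 11.2 says: "Details on the impact on the power will be described in the SAP and/or Clinical Study Report". SAP section 1.4, written in 2018 after the halt, gives a total of approximately 423 subjects. It states no revised limit or detection probability and refers the reader to protocol section 11.2. SAP section 7 pools Cohorts II and III for safety, presents Cohort I and Group 4 separately, and leaves subjects without a second dose out of the Post-dose 2 adverse event analysis.

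**The concern.** Safety is the primary objective, and no hypothesis is tested. What the trial can say about an event that does not occur therefore rests on the zero-event limit and on Table 7. Protocol section 11.2 and the synopsis are the only places in the supplied documents that give this limit.

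Two things looked wrong. The number behind the smallest limit does not fit the cohort table. It also exceeds the whole enrolment that the SAP reports. A reader who follows SAP section 1.4 back to protocol section 11.2 finds a precision that the trial cannot deliver. This trial was paused for a serious and very rare neurological event, so that reader is likely to look for exactly this figure.

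**Working it through.** **Reproducing the plan.** With no events in n subjects, the exact one-sided 97.5% upper limit is UL = 1 − 0.025^(1/n). The chance of seeing at least one event of true incidence p is 1 − (1 − p)^n.

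- n = 121: 3.00%; n = 174: 2.10%; n = 499: 0.737%. All lie below the printed bounds.
- Table 7 also reproduces. For example, n = 499 gives 39.3% at 0.1% incidence and 91.8% at 0.5% (printed 39% and 92%).

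So the formula is right, and the question is which n applies.

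**Double count.**

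1. Active subjects per group (Table 1): 10 + 84 + 80 = 174 across Cohorts I to III; 84 + 80 = 164 in Cohorts II and III.
2. 174 + 174 + 121 = 469, so the 469 includes the 20 Cohort I subjects of Groups 1 and 2. It cannot be a total for Cohorts II and III.
3. 469 + 30 = 499, so Cohort I is added a second time.
4. Cross-check against 543: 543 − 469 = 74 placebo, which is 30 + 30 + 14. But 543 − 499 = 44 placebo, fewer than the 60 planned in Groups 1 and 2 alone.
5. Group 3: the text does not say whether its 121 includes its 10 Cohort I subjects. If it does not, then 135 − 10 = 125 subjects in Cohorts II and III would hold 121 active and 4 placebo. The most active-heavy ratio, 14:1 in Cohort II, allows 125 × 14/15 = 116.7. The 121 therefore almost certainly includes them.
6. Corrected totals: 469 in Cohorts I to III and 469 − 30 = 439 in Cohorts II and III. On the less likely reading of Group 3 they are 479 and 449.

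| n | Meaning | Upper limit |
|---|---|---|
| 499 | as printed | 0.737% |
| 479 | Cohorts I–III, if the 121 excludes Cohort I | 0.767% |
| 469 | Cohorts I–III, Cohort I counted once | 0.783% |
| 460 | smallest n below 0.8% | 0.7987% |
| 459 | one fewer | 0.8005% |
| 449 | Cohorts II–III, if the 121 excludes Cohort I | 0.818% |
| 439 | Cohorts II–III | 0.837% |
| 423 | every subject in the stopped trial treated as active | 0.868% |

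**The stopped trial.** The 423 row needs no assumption about the active share. The documents do not give the number who received active vaccine, so a range is needed. Assume that Cohort I is all active and at most 30, Cohort II is 14/15 active and at most 270, Cohort III is 10/13 active and at most 312, and the 18 Group 4 subjects may lie inside or outside the 423.

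- Cohorts I–III, most active: 30 + 252 + 123 × 10/13 = 376.6 (Group 4 outside). UL at 377 = 0.974%.
- Cohorts I–III, fewest active: 240 + 93 × 14/15 = 326.8 (Group 4 inside, Cohort I empty). UL at 327 = 1.122%.
- Cohorts II–III, most active: 252 + 153 × 10/13 = 369.7. UL at 370 = 0.992%.
- Cohorts II–III, fewest active: 240 + 63 × 14/15 = 298.8. UL at 299 = 1.226%.
- Chance of seeing an event of 0.5% incidence: 80.6% at n = 327 and 84.9% at n = 377, against 92% printed for 499.
- Chance of seeing an event of 0.1% incidence: 27.9% and 31.4%, against 39% printed.

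The number boosted is not stated, so no Post-dose 2 limit can be calculated. It will be wider, since SAP section 1.4 says many subjects were not boosted.

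**Power statement.** With 164 against 121 − 10 = 111 subjects and a two-sided level of 0.05/3, the Table 8 differences have 80.0% to 82.5% power. The claim of 80% or more thus holds for the Amendment 4 plan.

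**The case against.** The limit is stated conditionally, for a sample of 499, and at that sample it is true. It remains true at the corrected 469. Section 11.2 also says that enrolment stops and defers the consequences to the SAP or the Clinical Study Report, so an SAP without the update breaches nothing. No printed limit is attached to the 469 label, and protocol section 11.4 plans safety summaries by cohort and overall, which suits an all-cohort denominator. SAP section 5.1 will tabulate how many subjects entered each period, so the denominators will appear with the results. No analysis set, endpoint or test depends on any of this.

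Most of that stands. The double count alone is a labelling error with almost no numerical effect, and the Clinical Study Report is a permitted place for the update. What does not stand is leaving SAP section 1.4 as it is. It was written with the total of 423 known, yet it sends the reader to the figure for 499 and does not say where a revised one will be.

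The range of 327 to 377 does depend on the planned ratios. Its low end sets Cohort I to zero, although SAP section 1.2 says that Cohort I started. Setting Cohort I at its full 30 moves the low end only to 30 + 240 + 63 × 14/15 = 328.8, about 329. The France-specific protocol that the SAP also cites was not supplied, so an update there cannot be ruled out.

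**Conclusion.** The point holds. Counted once, Cohort I gives 469 active subjects in Cohorts I to III and about 439 in Cohorts II and III under the Amendment 4 plan. The 499 is wrong under either reading of Group 3. For the pooled Cohorts II and III that SAP section 7 uses, even that plan does not give a limit below 0.8%: it gives 0.84%, or 0.82% on the less likely reading.

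For the stopped trial the limit is at least 0.87% on the SAP's own approximate total. Under the planned ratios and cohort maxima it is 0.97% to 1.12% for Cohorts I to III, and 0.99% to 1.23% for Cohorts II and III. The shift is modest and alters no analysis. It does affect the only stated precision for the primary objective, and the correct figures are all less favourable than the printed one.

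**What to change.** In protocol section 11.2, relabel 469 as Cohorts I to III. There and in the synopsis, replace 499 with 469, and delete the 499 column of Table 7, since the 469 column is already there. Mark the 0.8% limit and the 80% power statement as applying to the Amendment 4 plan only.

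In SAP section 1.4, give the zero-event 97.5% upper limits and the detection probabilities for the numbers actually primed and actually boosted, on the pooled Cohorts II and III, or state that the Clinical Study Report will give them. Power need not be recalculated, because no formal testing is planned. An expected confidence-interval half-width for the per-protocol numbers is enough for the ELISA endpoint.

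The cost is text only: no subjects, data or analyses are added. Changing the protocol requires a formal amendment under section 17.1. If none is planned, a short statement of the corrected counts in SAP section 1.4 carries the same information.
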